9.3.2 Analysis of Key Secondary Efficacy Endpoints

9.3.2.1 Definition of Key Secondary Efficacy Endpoints

The key secondary efficacy endpoints are as follows:

- Relative change in percent predicted FEV₁ from baseline through Week 8 in the Active Comparator Treatment Period
- Absolute change in Cystic Fibrosis Questionnaire–Revised (CFQ-R) respiratory domain score from baseline through Week 8 in the Active Comparator Treatment Period

Relative change in percent predicted FEV₁ from baseline through Week 8 in the Active Comparator Treatment Period

Relative change in percent predicted FEV₁ at each visit will be defined as the absolute change in percent predicted FEV₁ at each visit divided by the baseline percent predicted FEV₁ in the Active Comparator Treatment Period.

Absolute change in CFQ-R respiratory domain from baseline through Week 8 in the Active Comparator Treatment Period

The CFQ-R is a validated CF-specific instrument that measures quality-of-life domains. The details on the CFQ-R forms and the CFQ-R scoring manual are provided in [Appendix G](#).

9.3.2.2 Analysis of Key Secondary Efficacy Endpoints

Relative change in percent predicted FEV₁ from baseline through Week 8 in the Active Comparator Treatment Period

A model similar to the MMRM for the primary analysis of the primary efficacy endpoint will be used. Average relative change from baseline in percent predicted FEV₁ through Week 8 and the relative change from baseline in percent predicted FEV₁ at each post-baseline visit (Weeks 2, 4, and 8), including LS means, standard error (SE), and the 2-sided 95% confidence interval along with the *P* value, will also be derived from the MMRM model for the Active Comparator Treatment Period based on the FAS. The LS means (95% CI) at each visit will be plotted by treatment groups.

In addition, average raw values and average relative change from baseline in percent predicted FEV₁ through Week 8, and raw values and relative change from baseline in percent predicted FEV₁ at each visit (Weeks 2, 4, and 8) will be summarized using descriptive summary statistics.

The cumulative distribution plot of average relative change from baseline in percent predicted FEV₁ through Week 8 will be plotted by treatment groups. In addition, a bar chart showing the percentage of subjects by response categories (<-10%, ≥-10% to < -7.5%, ≥-7.5% to <-5%, ≥-5% to <-2.5%, ≥-2.5% to <0%, ≥0% to <2.5%, ≥2.5% to <5%, ≥5% to <7.5%, ≥7.5% to <10%, ≥10%) of average relative change from baseline in percent predicted FEV₁ through Week 8 will be plotted by treatment groups.

Absolute change in CFQ-R respiratory domain from baseline through Week 8 in the Active Comparator Treatment Period

Analysis for the absolute change from baseline in CFQ-R respiratory domain (Pooled 'Children Ages 12 and 13' Version and 'Adolescents and Adults' Version) through Week 8 will be similar to that used for the primary analysis, with the addition of the baseline CFQ-R respiratory domain score as a covariate. The primary result obtained from this model will be the average treatment effect through Week 8.

Absolute change from baseline in CFQ-R respiratory domain at each postbaseline visit (Week 4 and Week 8) will be derived from the same model. The LS means, SE, 95% CI, and *P*-values at each visit will be provided; LS means (95% CI) will be plotted by treatment

groups. In addition, average raw values and average absolute change from baseline in CFQ-R respiratory domain through Week 8, and raw values and absolute change from baseline in CFQ-R respiratory domain at each postbaseline visit (Week 4 and Week 8) will be summarized using descriptive summary statistics.

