**Table 3-1 Screening Period Assessments – Study VX14-661-109**

Sweat chloride j	X
Urinalysis	X
Hematology	X
Coagulation	X
Serum chemistry	X
Inclusion/exclusion criteria review	X
Prior and concomitant medications	X
AEs and SAEs	Continuous from signing of ICF and assent (where applicable) through Safety Follow-up Visit k

AE: adverse event; CFTR: cystic fibrosis transmembrane conductance regulator; CFQ-R: Cystic Fibrosis Questionnaire-Revised; ECG: electrocardiogram; FSH: follicle-stimulating hormone; ICF: informed consent form; PE: physical examination; ██████████ SAE: serious adverse event; ██████████

- j A sweat chloride test must be performed at the Screening Visit if an eligible sweat chloride value is not available in the subject’s medical records and the Screening Visit value is needed to establish eligibility. For subjects using sweat chloride values documented in their medical records to establish eligibility, the sweat chloride test at the Screening Visit is optional.
- k For enrolled subjects who do not have a Safety Follow-up Visit, AEs and SAEs will be collected through the earliest of the following: 28 days after the last dose of study drug; the ETT Visit, if that visit is 3 weeks or later following the last dose of study drug (Section 8.1.5); or prior to the first dose of study drug in the extension study.

**Table 3-2 Ivacaftor Run-in Period, Active Comparator Treatment Period, ETT, and Safety Follow-up Visit Assessments – Study VX14-661-109**

	Ivacaftor Run-in Period b		Active Comparator Treatment Period				ETT Visit c	Safety Follow-up Visit 28 days (± 7 Days) After Last Dose d
	Week -4 (Day -28 ± 2 Days)	Week -2 (Day -14) (± 2 Days)	Day 1	Week 2 (Day 15) (± 2 Days)	Week 4 (Day 29) (± 5 Days)	Week 8 (Day 57) (± 5 Days)		
Event/Assessment a	X	X	X	X	X	X	X	X
Clinic visit	X	X	X	X	X	X	X	X
Inclusion and exclusion criteria review	X							
CFQ-R e	X	X	X	X	X	X	X	X
Ophthalmologic examination f							X	X

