Randomized treatment dosing u			X	X	X			
Study drug count		X	X	X	X	X	X	X
Concomitant medications v	X	X	X	X	X	X	X	X

p PK blood samples will be collected at Week -2 (before the morning dose and at 2 and 6 hours after the morning dose) and Week 2 (before the morning dose and at 3 and 8 hours after the morning dose). If study drug is not administered at the Week -2 Visit or Week 2 Visit (i.e., study drug interruption or permanent discontinuation of study drug), a single PK blood sample will still be collected. At the ETT and the Safety Follow-up Visits (as applicable), a PK blood sample will also be collected.

Randomization must occur after all inclusion and exclusion criteria are met, after the 4 weeks Ivacaftor Run-in Period, and before the first dose of study drug on Day 1 of the Active Comparator Treatment Period. Randomization will be done through IWRS.

s Fat-containing food such as a “standard CF” high-fat, high-calorie meal or snack, will be provided at the site to subjects after all predose assessments have been completed.

t Subjects will receive ivacaftor 150 mg q12h from the Week -4 Visit through the evening of Day -1 (1 day prior to the Day 1 Visit). The study drug should be administered every 12 hours (± 2 hours) within 30 minutes after starting a meal with fat-containing food such as a “standard CF” high-fat, high-calorie meal or snack. On days of scheduled visits, the morning dose of study drug will be administered at the site after predose assessments have been completed.

u Subjects will receive randomized study treatment from randomization through the evening of the day before the Week 8 Visit. The study drug should be administered every 12 hours (± 2 hours) within 30 minutes after starting a meal with fat-containing food such as a “standard CF” high-fat, high-calorie meal or snack. On days of scheduled visits, the morning dose of study drug will be administered at the site after predose assessments have been completed.

v Information on concomitant medications is collected through the Safety Follow-up Visit for all subjects. For subjects who discontinue treatment and are followed for certain efficacy assessments after the ETT Visit (see Section 8.1.5), information on concomitant antibiotic therapy for “sinopulmonary signs/symptoms” are collected through the Week 8 Visit, as described in Section 11.6.4.1.1

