7.2 Sample Size and Power

The primary efficacy endpoint is the absolute change in percent predicted FEV₁ from baseline through Week 8 in the Active Comparator Treatment Period.

The null hypothesis to be tested is that the mean absolute change in percent predicted FEV₁ from baseline through Week 8 in the Active Comparator Treatment Period is the same for the VX-661/ivacaftor combination therapy and the ivacaftor monotherapy. Assuming a common standard deviation (SD) of 7 percentage points and a 10% dropout rate, a sample size of 160 subjects will have at least 80% power to detect a treatment difference of 3.4 percentage points between treatment arms in absolute change in percent predicted FEV₁ at a 2-sided 0.05 significance level. A *P* value of 0.05 or less will be interpreted as sufficient evidence to

reject the null hypothesis. The assumption of the main treatment effect of VX-661/ivacaftor combination therapy over ivacaftor monotherapy and a 7 percentage point SD is based on the results from the Phase 2 Study 101, Group 7.

With 160 subjects and assuming 10% lost to follow-up, the study has limited power to detect a treatment effect in CFQ-R respiratory domain score, i.e., a power of 32% to detect a treatment effect (SD) of 4 (16) in absolute change in CFQ-R respiratory domain score. The assumptions regarding the treatment effect of VX-661/ivacaftor combination therapy over the ivacaftor monotherapy and the SD are all based on the within-group treatment effects observed in the Phase 2 Study 101, Group 7.

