9 STATISTICAL ANALYSIS

9.1 General Considerations

The Schedule of Assessments is provided in [Appendix C](#). The precision standards for reporting safety and efficacy variables are provided in an internal Biometrics document that specifies the programming rules including the precision for derived variables.

All individual subject data for subjects who were randomized or received at least 1 dose of study drug, i.e., All Subjects Set, will be presented in data listings, with indicator of dosing period, i.e., Ivacaftor Run-in Period vs. Active Comparator Treatment Period, as applicable. Listings related to Active Comparator Treatment Period only will be based on the Active Comparator Subjects Set.

Continuous variables will be summarized using the following descriptive summary statistics: the number of subjects (n), mean, standard deviation (SD), standard error (SE), median, minimum value (min), and maximum value (max).

Categorical variables will be summarized using counts and percentages.

Baseline value, Absolute change from baseline and Relative change from baseline will be defined separately for the Ivacaftor Run-in Period and the Active Comparator Treatment Period:

Baseline value:

- Unless specified otherwise, baseline for the Ivacaftor Run-in Period will be defined as the most recent non-missing measurement (scheduled or unscheduled) collected prior to initial administration of Ivacaftor monotherapy.
- Unless specified otherwise, the baseline for the Active Comparator Treatment Period will be defined as the most recent non-missing measurement (scheduled or unscheduled) collected prior to initial administration of the VX-661/ivacaftor combination therapy or ivacaftor monotherapy (placebo/ivacaftor) during the Active Comparator Treatment Period, but no earlier than the measurement at Week -2.
- For spirometry, the baseline value used for the Active Comparator Treatment Period will be the average of the measurement at Week -2 and the measurement on Day 1 predose. If a subject has an AE leading to an approved extension of the Ivacaftor Run-in Period, and the Week -2 spirometry assessment is between the start and end date (inclusive) of the AE, then the measurement on Day 1 predose will serve as baseline for the Active Comparator Treatment Period.
- For ECG, the baseline will be defined as the average of the non-missing pretreatment measurements (triplicate) on Day 1 (the first day) of the corresponding treatment period.

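### The CFQ-R analysis uses one of two pre-randomisation scores taken on ivacaftor; adding the Week -2 score as a second covariate is an optional, nearly free gain in precision of uncertain size

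*SAP*

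**What the plan says.** **Collection.** Protocol Table 3-2 marks the CFQ-R at every visit, including Week -2 and Day 1. Both fall on run-in drug and before the first randomised dose: "Subjects will receive ivacaftor 150 mg q12h from the Week -4 Visit through the evening of Day -1". The window table in SAP Appendix D also has a Week -2 entry for the CFQ-R.

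**Baseline.** The default in SAP 9.1 is that "the baseline for the Active Comparator Treatment Period will be defined as the most recent non-missing measurement (scheduled or unscheduled", taken before the first randomised dose and no earlier than Week -2. SAP 9.1 then lists exceptions for spirometry, ECG and sweat chloride. For spirometry the baseline "will be the average of the measurement at Week -2 and the measurement on Day 1 predose". No exception is listed for the CFQ-R, so its baseline is normally the Day 1 score, with Week -2 as a fallback.

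**Model.** SAP 9.3.2.2 uses a model similar to the primary one, "with the addition of the baseline CFQ-R respiratory domain score as a covariate". The post-baseline visits are Weeks 4 and 8: "Absolute change from baseline in CFQ-R respiratory domain at each postbaseline visit (Week 4 and Week 8) will be derived from the same model". Protocol 12.3.3.2 describes the same single-baseline adjustment.

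**Power.** SAP 7.2 says that "the study has limited power to detect a treatment effect in CFQ-R respiratory domain score", and puts it at "a power of 32% to detect a treatment effect (SD) of 4 (16) in absolute change in CFQ-R respiratory domain score", with 160 subjects and 10% lost to follow-up. The endpoint is third and last in the testing hierarchy (SAP 9.3.6).

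**The concern.** The run-in exists to give a reliable on-ivacaftor baseline, and for spirometry the plan uses two run-in visits to obtain it. The CFQ-R is completed at the same two visits, yet only the later score normally reaches the treatment comparison. A second pre-randomisation reading can help predict the post-baseline scores and so reduce residual variance. It cannot bias the comparison, because it precedes randomisation.

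The stake is precision only. The planned standardised effect is 4/16 = 0.25 for the CFQ-R, against 3.4/7 = 0.49 for percent predicted FEV1 (SAP 7.2), so the CFQ-R comparison has the most to gain from extra precision. Validity and Type I error are not in question. The point concerns the Week -2 form before randomisation, not the Week 2 form after it.

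**Working it through.** **Inputs from SAP 7.2.** Effect 4; SD of change 16; 160 subjects randomised 1:1; 10% lost, so 160 × 0.9 / 2 = 72 per arm; two-sided 5% level.

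**Assumption.** The documents give no visit-to-visit correlation for the CFQ-R. I take a common correlation *r* of 0.5 to 0.8 first, then less favourable structures. Covariates other than the CFQ-R are left out.

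**Step 1: the plan's own figure.** The standard error of the difference is 16 × √(2/72) = 16/6 = 2.667, and 4/2.667 = 1.50. Power is Φ(1.50 − 1.96) = Φ(−0.46), or 32.3% with the negligible opposite tail; the noncentral *t* gives 31.9%. The stated 32% is reproduced. It is the power of an unadjusted comparison of change scores, not of the planned covariate-adjusted model.

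**Step 2: residual variance under equal correlation.** Let *Y* be the mean of the Week 4 and Week 8 scores, and s² the variance of one score.

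- Var(*Y* − Day 1) = 1.5 s²(1 − r). Setting this to 16² = 256 gives s² = 512 / [3(1 − r)].
- Given Day 1 only: s²[(1 + r)/2 − r²] = 256(1 + 2r)/3.
- Given Day 1 and Week -2: s²[(1 + r)/2 − 2r²/(1 + r)] = 256(1 + 3r) / [3(1 + r)].
- Ratio: (1 + 3r) / [(1 + r)(1 + 2r)].

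Power is Φ(4 / (SD/6) − 1.96), with SD the square root of the residual variance.

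| r | Variance, Day 1 only | Variance, both | Ratio | Power, Day 1 only | Power, both |
|---|---|---|---|---|---|
| 0.5 | 170.7 | 142.2 | 0.833 | 45.1% | 52.1% |
| 0.6 | 187.7 | 149.3 | 0.795 | 41.8% | 50.2% |
| 0.7 | 204.8 | 155.6 | 0.760 | 38.9% | 48.6% |
| 0.8 | 221.9 | 161.2 | 0.726 | 36.4% | 47.2% |

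Residual variance falls by 17% to 27%, and power rises by about 7 to 11 points from the planned model.

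**Step 3: less favourable structures.**

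- *Stable plus decaying component plus noise.* The cut is about 4% to 14%, depending on the mix. For example, with 40% of variance stable, 40% decaying (correlation 0.5 at four weeks) and 20% noise, residual variance goes from 181.9 to 170.3 (ratio 0.936) and power from 42.8% to 45.2%.
- *Decay plus 15% noise, no stable component.* The cut is 0.2% to 13%, for four-week correlation 0.4 to 0.8.
- *Pure AR(1) decay.* Given Day 1, the Week -2 score carries no further information. The ratio is exactly 1.

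**Step 4: averaging instead.** Under equal correlation the mean of the two scores does as well as two separate covariates. Under pure AR(1) with four-week correlation 0.4 to 0.8, it raises residual variance by 2% to 7% and costs about 1 to 2 points of power. Separate covariates avoid this, at the price of one degree of freedom.

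**The case against.** The strongest reply is that nothing is wrong. Protocol 12.3.1 and SAP 9.1 give the same default rule for the CFQ-R, both documents prespecify baseline adjustment, and spirometry is the only measure with a baseline drawn from two visits. Using Day 1 is a legitimate choice, the gain rests on an assumed correlation, and the limited power is disclosed. All of that stands, and it is why this is a suggestion and not a defect.

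Four stronger readings are tempting, and the documents do not support them.

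- *Power would rise from 32% to about 50%.* The 32% is for an unadjusted change score. The planned adjusted model already has about 36% to 45% under the equal-correlation assumptions, and gains must be counted from there.
- *Noise in the single baseline passes in full into the comparison.* That describes an unadjusted change score. With Day 1 as a covariate, residual variance is already 13% (r = 0.8) to 33% (r = 0.5) below 256.
- *A questionnaire varies more between visits than spirometry, so a second reading is worth at least as much.* Neither document says so. The SDs of 16 and 7 are on different scales and describe change, not visit-to-visit reliability.
- *The Week -2 score is never used.* It becomes the baseline when Day 1 is missing, and SAP 9.3 allows run-in summaries.

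Three limits also stand. Subjects new to ivacaftor have had only two weeks of drug at Week -2, so variable early response could shrink the gain. The model also adjusts for age group, mutation type and baseline percent predicted FEV1, and any information these share with the Week -2 score is not in the calculation. SAP Appendix G, on CFQ-R forms and scoring, is not in the text available here; a separate baseline rule there cannot be excluded, though SAP 9.1 lists none.

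**Conclusion.** The plan is valid as written, but it may leave precision unused on its only patient-reported key secondary endpoint. With 72 per arm, effect 4 and SD of change 16, the reduction in residual variance from adding Week -2 is 17% to 27% under equal correlation, about 4% to 14% under mixed structures, and about 0% under pure AR(1). The correlation structure is an assumption throughout, and equal correlation is the most favourable case considered. Even there power reaches only about 47% to 52%, so the endpoint stays underpowered. This is an optional improvement and does not change any conclusion about the adequacy of the trial.

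**What to change.** In SAP 9.3.2.2, keep the endpoint as change from the Day 1 baseline and add the Week -2 CFQ-R respiratory domain score as a second, separate baseline covariate.

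Prespecify the handling of a missing Week -2 score: fill it using baseline data only, for example with the subject's Day 1 score. Without such a rule the mixed model drops any subject who lacks the covariate, and SAP 9.1 does not impute unless told to. Losing 4% of subjects in this way would roughly cancel a 4% reduction in variance.

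Do not use the average of the two scores as the covariate, even though that would mirror the spirometry rule, because it can lose precision (Step 4).

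The change must be made before database lock and unblinding, and the SAP should record it as an addition to the model summarised in Protocol 12.3.3.2. It costs about one degree of freedom and two sentences of text, with no new data, visits or subjects.

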9.3.3 Analysis of Secondary Efficacy Endpoints

9.3.3.1 Definition of Secondary Efficacy Endpoints

Absolute change from baseline in sweat chloride from baseline through Week 8 in the Active Comparator Treatment Period

For each subject and at each time point, 2 sweat chloride measurements will be collected: 1 from the right arm, and 1 from left arm. Only the sweat chloride values obtained from a sample volume ≥ 15 μL will be used in any analysis.

Note: A volume of ≥ 15 μL is required for an accurate determination of sweat chloride. Any results reported having volume < 15 μL or “Quantity Not Sufficient” (QNS) will be considered missing.

The sweat chloride results for the left and right arms will be averaged and used in the analysis provided that the sweat chloride volumes for the left and right arms are both ≥ 15 μL ; if only 1 arm has a volume ≥ 15 μL , then only that value will be used. If a subject has replicated measurements at a post-baseline time point, then the median of the values will be used in data analyses.

Note any sweat chloride values reported as < 10 mmol/L or > 160 mmol/L Values > 160 mmol/L or < 10 mmol/L will be set to missing and excluded from the analysis because these values are considered clinically impossible.

9.3.3.2 Analysis of Secondary Efficacy Endpoints

Absolute change from baseline in sweat chloride from baseline through Week 8 in the Active Comparator Treatment Period

A model similar to the MMRM for the primary analysis of the primary efficacy endpoint will be used with the addition of baseline sweat chloride as a covariate. Average absolute change from baseline in sweat chloride through Week 8 and absolute change from baseline in sweat chloride at each post baseline visit (Weeks 4 and 8), including LS means, standard error (SE), and the 2-sided 95% confidence interval along with the *P* value, will be derived from the main model based on the FAS. The LS means (95% CI) at each visit will be plotted by treatment groups.

In addition, average raw values and average absolute change from baseline in sweat chloride through Week 8, and raw values and absolute change from baseline in sweat chloride at each visit (Week 4 and Week 8) will be summarized using descriptive summary statistics.

9.3.6 Multiplicity Adjustment

A hierarchical testing procedure will be used to control the Type I error at two-sided $\alpha = 0.05$ among the primary and key secondary endpoints. For a test at any step to be considered statistically significant within the testing hierarchy, it must be statistically significant, and all previous tests (if any) within the hierarchy must be statistically significant, at the 0.05 level. The testing hierarchy is as follows:

1. Absolute change in percent predicted FEV₁ from baseline through Week 8
2. Relative change in percent predicted FEV₁ from baseline through Week 8
3. Absolute change in CFQ-R respiratory domain score from baseline through Week 8

9.4 Safety Analysis

Safety endpoints will be analyzed separately for the Ivacaftor Run-in Period and the Active Comparator Treatment Period based on the corresponding Safety Set. Only descriptive summaries of safety will be provided (i.e., no statistical testing will be performed).

The overall safety profile of study drug will be assessed in terms of the following safety and tolerability endpoints:

- Adverse events
- Clinical laboratory values (hematology, serum chemistry, coagulation studies, and urinalysis)
- Standard 12-lead electrocardiograms
- Vital signs
- Pulse oximetry

The safety profile will also include the following safety-supporting data

- Weight
- BMI
- Ophthalmological Examination

